#### **10.3.5.2 Treatment-emergent death**

The number and percentage of treatment-emergent deaths will be described by SOC and PT up to EOT + 3 days.

In addition, all deaths reported during the study will be listed.

#### **10.3.5.3 Laboratory variables**

All laboratory data transferred are taken into account regardless of whether they correspond to scheduled (per protocol) or unscheduled assessments. All recorded assessments will be assigned to the most appropriate visit time points according to the best fitting time-window for that assessment using the usual location and scale summary statistics.

For each laboratory variable, the number and percentage of participants with at least one treatment-emergent marked abnormality will be summarized up to EOT + 3 days.

The change in selected laboratory values and the change in TSH will also be summarized over time up to EOT + 3 days, using the same descriptive statistics for continuous variables.

#### **10.3.5.4 ECG**

For each ECG variable, the number and percentage of participants with at least one treatment-emergent marked abnormality will be summarized up to EOT + 3 days.

#### **10.3.5.5 Vital signs**

Absolute values and changes from baseline will be summarized over time up to EOT + 3 days, using descriptive statistics for continuous variables.

#### **10.3.5.6 Height and Weight**

Absolute values and changes from baseline will be summarized over time up to EOT + 3 days, using descriptive statistics for continuous variables.

#### **10.3.5.7 Sexual maturation**

Absolute values and changes from baseline will be summarized over time up to EOT + 3 days, using descriptive statistics for continuous variables.

### **10.3.6 Analysis of the exploratory efficacy variables**

All analyses of exploratory variables will be carried out descriptively using the FAS and will be performed as follows:

- In the overall population.
- By iMTD dose groups.
- By age cohort.

The main exploratory analysis will be based on observed data, with no imputation rules. Sensitivity analyses will be performed by imputing missing values as appropriate and will be described in the SAP.

#### **10.3.6.1 Time to disease progression / clinical worsening**

Event time is defined as the time elapsed from the first study drug administration to the day of the occurrence of the event. Time to event endpoints will be presented as Kaplan Meier estimates with two-sided 95% CIs at relevant time points and displayed in both a graphical (where the number of participants at risk is at least 10% of the total number of participants in the Analysis Sets) and a tabular form. Participants who did not experience an event will have their event time censored at EOT + 7 days. The number of participants at risk, the number of participants censored and the number of participants with event will be displayed.

#### **10.3.6.2 NYHA / WHO FC**

The proportion of participants having worsened, remained unchanged, or improved will be calculated at each time point of assessment and up to the timepoint with at least 10 participants in the cohort. Two-sided 95% CIs of the proportions will be presented.

#### **10.3.6.3 6MWD**

The change from baseline will be summarized at each time point of assessment up to the timepoint with at least 10 participants in the cohort, using descriptive statistics for continuous variables. Two-sided 95% CIs of the mean and median will also be provided.

#### **10.3.6.4 Panama FC**

The proportion of participants having worsened, remained unchanged, or improved will be calculated at each time point of assessment up to the timepoint with at least 10 participants in the cohort. Two-sided 95% CIs of the proportions will be presented.

#### **10.3.6.5 NT-proBNP**

The percent of baseline will be summarized at each time point of assessment and up to the timepoint with at least 10 participants in the cohort, using descriptive statistics for continuous variables on the log-transformed data. The resulting mean and two-sided 95%

CIIs will be inversely transformed using the exponential function to provide the geometric mean and corresponding two-sided 95% CIIs.

#### **10.3.6.6 Echo/Doppler**

The change from baseline to each time point of assessment for each Echo/Doppler variable will be summarized at each point of assessment up to the timepoint with at least 10 participants in the cohort, using descriptive statistics for continuous variables. The two-sided 95% CIIs of the means will also be provided.

#### **10.3.7 Analysis of the other variables**

All analyses of other variables will be carried out descriptively using SAS (Statistical Analysis System) and will be performed as follows:

- In the overall population.
- By iMTD dose groups.
- By age cohort.

The iMTD is defined as the last dose received before the Week 12 visit (for participants who prematurely discontinued study drug) or the dose received the day of the Week 12 visit (for participants who completed the 12-week up-titration period).

##### **10.3.7.1 Palatability and acceptability**

The palatability and acceptability of selexipag will be summarized separately with counts and percentages.

#### **10.4 Interim analyses**

An IDMC will be involved in the study to periodically review safety data and, if requested, PK data [see Section 3.3].

As described in Section 3.1, two interim PK analyses will be performed. They will be detailed in the modeling data analysis plan.

Additional assessments of PK profiles and interim analyses may be performed, as deemed appropriate by the sponsor.

#### **10.5 Sample size**

Based on clinical trial simulations using the population PK model of the GRIPHON study, at least 15 participants between  $\geq 12$  and  $< 18$  years of age (Cohort 1), at least 15 participants between  $\geq 6$  and  $< 12$  years of age (Cohort 2), and 10 participants between  $\geq 2$  and  $< 6$  years of age (Cohort 3) with evaluable PK profiles are necessary to obtain a 90% confidence interval of the  $AUC_{\tau,ss,combined}$  within a 1.4-fold range above or below the predicted median [see Section 14.7 Appendix 7].

PK data of pediatric participants with PAH in the planned clinical trial were simulated using the GRIPHON population PK model by appropriate assumptions of body weights. The body weight impact on PK model parameters was used as determined based on adult data. PK parameters were re-estimated 100 times and  $AUC_{\tau,ss,combined}$  was simulated 1,000 times, taking the parameter estimation uncertainty into account to determine  $AUC_{\tau,ss,combined}$  prediction uncertainty. This assessment of the  $AUC_{\tau,ss,combined}$  prediction uncertainty was performed for each planned interim analysis and the final analysis to check that at each stage the  $AUC_{\tau,ss,combined}$  for the respective cohort could be determined with sufficient accuracy.

The sample size is determined based on the assumption that the PK characteristics have the same inter-individual variability in pediatric as in adult participants with PAH. Furthermore, it is assumed that pediatric participants with PAH of the same weight as adult participants with PAH have the same PK, as relevant metabolic and elimination pathways are assumed to be mature and thus the PK modeling can partly be built on results from the GRIPHON study. At the interim analyses and the final PK analysis, all available PK data will be used to update the PK model and to confirm or adjust the dose selection. The emerging results will also be used to reconsider the sample size, with the aim of minimizing it. However, if the quality of the data collected does not allow for a sufficiently precise confirmation of body weight-based doses, additional participants may need to be enrolled in the study. More details on interim analyses will be provided in the modeling data analysis plan.

Based on the pediatric PK data available at the second interim analysis, the planned sample size for Cohort 3 (N 10) was assessed using a simulation/estimation approach. Pediatric datasets were simulated with fold-deviations of exposures ( $AUC_{\tau,ss,combined}$ ) of 0.5, 0.7, 1, 1.3, and 1.5-fold compared to the adult reference model [[PK Interim Analysis Report-2 AC-065A203 2020](#)]. Based on this analysis, the power of recognizing a pediatric to adult ratio of 0.5, 0.7, 1.3, and 1.5 as significantly different from 1, is predicted to be >99%, 82.8%, 56.4%, and 83.2%, respectively. Type 1 error (i.e., when the AUC ratio is 1) is estimated to be 11.8%. If the sample size of Cohort 3 is increased to 15, the estimated values of the power are predicted to be >99%, 91.6%, 71.2% and 96.2% for the exposure ratios of 0.5, 0.7, 1.3, and 1.5, respectively, and the Type 1 error is estimated to be 11.0% [[PK Interim Analysis Report-2 AC-065A203 2020](#)]. Based on this assessment, the planned sample size for Cohort 3 has been increased to at least 15 PK evaluable participants in order to ensure a power of at least 70% for all potential outcomes.

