Results of this model-based analysis will be used to confirm or adjust the selexipag doses initially selected. If the population PK model results suggest that the administered selexipag doses lead to exposures deviating from the currently predicted target exposures, the recommended starting dose, increments of up-titration, and maximum allowed dose (equivalent to 1,600 µg b.i.d. in adult participants with PAH) for the remaining participants to be enrolled in Cohort 2 and Cohort 3 will be adjusted. The decision on dose-adjustment will take into account the inter-individual variability in the pediatric population and the difference in exposure between lower and upper limits of body weight in the GRIPHON study. The inter-individual variability in the GRIPHON study was more than 30% (comparing the 10th and 90th percentiles), and difference in exposure between lower and upper limits of body weight was 50% [[Modeling and Simulation Report AC-065A302 \(GRIPHON\) 2014](#)]. It is expected that the dosing regimen does not need to be adjusted if the revised point estimate body weight-starting dose relationship deviates from the current estimate by less than 30%. The dosing regimen must be adjusted if the revised point estimate body weight-starting dose relationship deviates from the current estimate by more than 50%. If this difference between the revised and the current point estimate is between 30% and 50%, the decision on dose adjustment will depend on the results of safety assessments after the first dose. Enrollment of Cohort 3 (children  $\geq 2$  to  $< 6$  years of age) will start once the appropriate doses have been confirmed by modelling and simulation in a second interim analysis of PK data from the children older than 6 years (i.e., Cohorts 1 and 2), and if there is no safety concern based on IDMC reviews.

The PK data pooled from all three age cohorts will be modelled to allow dosing recommendations for all children  $\geq 2$  years of age. A final PK analysis will be prepared based on the overall PK and safety data up to Week 16 evaluation.

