Given the rareness of pediatric PAH, combined with the ongoing global Corona virus disease-2019 (COVID-19) pandemic, enrolling participants in age Cohort 3 ( $\geq 2$  to  $< 6$  years of age) into this study has been difficult and as such the planned sample size of at least 15 PK evaluable Cohort 3 participants remains a challenge. The option of confirming the selexipag dosing recommendation for participants aged  $\geq 2$  to  $< 6$  years based on a smaller sample size is, therefore, being considered. To assess this, a third interim PK analysis may be conducted, as deemed appropriate by the sponsor.

All available PK and safety data from participants in Cohorts 1, 2, and 3 up to Week 16 at the time of the data cut-off date, will be included in interim analysis 3. The analytical approach for interim analysis 3 will be the same as applied for interim analyses 1 and 2. For the dosing confirmation of Cohort 3 with fewer than the planned 15 PK evaluable participants, one of the following criteria is to be achieved:

- The 90% CI of the point estimate describing the body weight-starting dose relationship relative to the current estimate is within 0.70-1.30.

*Or*

- The 90% CI of the point estimate describing the body weight-starting dose relationship relative to the current estimate is within 0.50-1.50 and at the same time, no dose adjustment is warranted by the available safety data.

If, however, the 90% CI of the relative point estimate exceeds 0.70-1.30 and a dose adjustment may be warranted by the available safety data or the 90% CI of the relative point estimate exceeds 0.50-1.50, a final PK analysis including the PK data pooled from all 3 age cohorts and at least 15 PK available participants in Cohort 3, will be conducted. Following this final PK analysis, the dosing recommendation will be confirmed based on the revised point estimate body weight-starting dose relationship, irrespective of the 90% CI, as originally planned.

In case the dosing recommendation for age Cohort 3 is confirmed based on the third interim PK analysis, further enrolment into the trial will be terminated. The PK of all enrolled participants, including participants completing their PK assessments after the data cut-off date for interim analysis 3 will be included in the PK analysis to be reported in the clinical study report (CSR).

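### Section 10.5 promises at least 70% power in Cohort 3 for every outcome, but the figure belongs to a test of exposure ratio 1 with at least 15 children, not to the dose rules in Section 3.1 or to interim analysis 3 below 15

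*Protocol*

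**What the plan says.** Protocol Section 10.5 describes a simulation/estimation exercise run on the data available at the second interim analysis. It defines power as "the power of recognizing a pediatric to adult ratio of 0.5, 0.7, 1.3, and 1.5 as significantly different from 1". With 10 children in Cohort 3 the power "is predicted to be >99%, 82.8%, 56.4%, and 83.2%, respectively"; with 15 it is >99%, 91.6%, 71.2% and 96.2%, with a type 1 error of 11.0%. The section concludes that the size was "increased to at least 15 PK evaluable participants in order to ensure a power of at least 70% for all potential outcomes".

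Section 3.1 sets out how dosing is decided.

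- **Point-estimate zones.** No change to the regimen is expected if "the revised point estimate body weight-starting dose relationship deviates from the current estimate by less than 30" per cent. The regimen "must be adjusted if the revised point estimate body weight-starting dose relationship deviates from the current estimate by more than 50" per cent. Between the two, safety results decide.
- **Interim analysis 3 (optional, Amendment 7).** "For the dosing confirmation of Cohort 3 with fewer than the planned 15 PK evaluable participants", the 90% CI of the relative point estimate must lie within 0.70-1.30, or within 0.50-1.50 with no dose adjustment warranted by the safety data. If the dosing is "confirmed based on the third interim PK analysis, further enrolment into the trial will be terminated".
- **Final analysis with at least 15.** If interim 3 does not meet its criteria, "the dosing recommendation will be confirmed based on the revised point estimate body weight-starting dose relationship, irrespective of the 90% CI".

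The preceding paragraphs of Section 10.5 give a second assurance: 15, 15 and 10 evaluable participants in Cohorts 1 to 3 are needed for a 90% CI of the combined exposure within 1.4-fold of the predicted median, with a reference to Appendix 7. Section 10.3.2.1 marks hypotheses for the primary PK variable as not applicable. SAP Section 1 places PK modelling in separate plans.

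**The concern.** The power sentence is the stated reason for the size of the youngest cohort, whose dose confirmation is part of the primary objective. A reader will take it to mean that, whatever the true exposure, the study has at least a 70% chance of reaching the right conclusion about the starting dose. It does not say that.

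- The simulated test asks whether the exposure ratio differs from 1. Neither the point-estimate zones nor the CI-containment criteria are that test, and a power for one does not transfer to the other.
- The word *ensure* depends on reaching 15. Section 3.1 now allows a route that stops below 15, and Section 10.5 was not adjusted to say so.
- The simulations are on the exposure scale, while the 30% and 50% limits are on the body weight-starting dose relationship. The protocol does not say how one maps to the other.

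**Working it through.** **1. Reproduce the stated figure.** At n = 15 the four powers in Section 10.5 are >99%, 91.6%, 71.2% and 96.2%. The minimum is 71.2%, so at least 70% is correct for those four ratios and that test. At n = 10 the minimum is 56.4%, and ratio 1.3 is the only scenario below 70%.

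**2. Compare the test with the decisions.**

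| Decision | Criterion in Section 3.1 | Cohort 3 size |
|---|---|---|
| Dose rule and final analysis | Point estimate against 30% and 50% | At least 15 at the final analysis |
| Interim 3 | 90% CI within 0.70-1.30, or within 0.50-1.50 plus safety | Fewer than 15 |
| Power statement in 10.5 | Exposure ratio significantly different from 1 | 15 |

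No row of Section 3.1 matches the last row in its criterion, and interim 3 does not match it in sample size either.

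**3. Illustrate what happens at the 30% limit.** Assume the estimated ratio is log-normal with standard error SE on the log scale. The documents do not give SE, so I use two values.

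- Lower value, solved from the n = 15 power at ratio 1.3 with an assumed two-sided 10% level: SE = ln(1.3) / (z at 0.712 + z at 0.95) = 0.2624 / (0.559 + 1.645) = 0.119. The powers at 0.7 and 1.5 give 0.118 and 0.119.
- Upper value, from Appendix 7 Table 6 (17 kg, mean 1.39-fold from median to 95th percentile, 10 in Cohort 3): SE = ln(1.39) / 1.645 = 0.3293 / 1.645 = 0.20. This comes from a different simulation and serves only to widen the range.

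There are two readings of the scale. *Inverse*: dose ratio = 1 / exposure ratio, which follows if exposure is proportional to dose, as Section 3.2 assumes. *Direct*: the relative estimate is read as the exposure ratio itself.

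At true exposure ratio 1.3:

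- Inverse: the centre is ln(1/1.3) = -0.2624 and the lower limit is ln(0.70) = -0.3567, a gap of 0.0943. With SE 0.119, z = 0.79 and the chance of passing 30% is 21%. With SE 0.20, z = 0.47; both tails together give 32%.
- Direct: the centre is ln(1.3), which is the limit itself, so the chance is 50% whatever the SE.

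The same calculation for the three ratios with a definite stated power:

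| True exposure ratio | Stated power, n = 15 | Beyond 30%, inverse (SE 0.119 / 0.20) | Beyond 30%, direct (SE 0.119 / 0.20) |
|---|---|---|---|
| 0.7 | 91.6% | 79% / 68% | 50% / 50% |
| 1.3 | 71.2% | 21% / 32% | 50% / 50% |
| 1.5 | 96.2% | 66% / 60% | 88% / 76% |

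On neither reading does 70% hold at every simulated ratio.

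**4. Limits of the illustration.** The implied standard deviation, 0.119 × √15 = 0.46, reproduces the n = 15 powers (91.3%, 71.4%, 96.2% for ratios 0.7, 1.3 and 1.5). It does less well at n = 10, where it gives 79.0%, 56.3% and 87.3% against the stated 82.8%, 56.4% and 83.2%. The percentages in step 3 are therefore indicative only.

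**5. The 1.4-fold precision.** Appendix 7 Table 6, with 10 in Cohort 3:

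| Weight | Median | Mean | Maximum |
|---|---|---|---|
| 17 kg | 1.38 | 1.39 | 1.60 |
| 35 kg | 1.23 | 1.23 | 1.34 |
| 59 kg | 1.34 | 1.34 | 1.61 |

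The mean is below 1.4 at every weight, but some simulated trials exceed it at 17 kg and 59 kg. Appendix 7 says *on average*; Section 10.5 does not.

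**The case against.** The strongest reply is that nothing is miscalculated. Read within its paragraph, *all potential outcomes* means the four ratios just listed, the test is defined there, and 71.2% exceeds 70%. Sizing an estimation study by its ability to detect a departure from 1 is a legitimate planning device and need not mirror the decision rule. Section 10.5 explains the planned size and does not assign 70% to interim 3. Interim 3 has its own CI criteria, which wide intervals at small n tend to fail, and a return to at least 15 if they are not met. Section 10.5 also points to Appendix 7 for the precision figure.

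Most of this stands. The numbers are sound, and interim 3 is not unguarded. What remains is that the closing sentence claims more than its paragraph supports, and that the amended design no longer guarantees the sample size on which the claim depends.

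Some stronger inferences should be resisted:

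- *The power figures are wrong.* The rates in step 3 answer a different question and do not contradict them.
- *Ratio 1.3, which drove the increase to 15, is only a 23% dose deviation where no adjustment is expected, and no scenario tests the mandatory-adjustment zone for excess exposure.* Both follow only on the inverse reading. The simulated grid of 0.5, 0.7, 1.3 and 1.5 coincides with the 30% and 50% limits, so the direct reading is also plausible.
- *The 70% is the only assurance given.* The 1.4-fold precision is a second one, and it bears on both point estimates and intervals.
- *Nobody has calculated the behaviour of the dose rules.* The modelling data analysis plan or the second PK interim report may contain it; neither is available here.

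**Conclusion.** The concern holds as a matter of scope. The assurance of at least 70% (minimum 71.2%) is valid for finding the exposure ratio different from 1 at true ratios 0.5, 0.7, 1.3 and 1.5 with 15 evaluable children in Cohort 3. It does not describe the point-estimate zones or the interim 3 CI criteria, and it is not secured if interim 3 closes enrolment below 15. For scale, the same test has 56.4% power at n = 10 and ratio 1.3.

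These conclusions rest on the protocol's own text and figures. The rates of about 21-32% (inverse) or about 50% (direct) for passing the 30% limit at ratio 1.3 are illustrations. They depend on a log-normal estimate, an SE between 0.119 and 0.20, and an assumed 10% two-sided level in deriving the lower SE. They are enough to show that 70% does not carry over on either reading, but not to estimate the true rates. The missing qualification on the 1.4-fold precision is a smaller instance of the same overstatement.

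None of this shows that Cohort 3 is too small or that the dose limits are unsuitable.

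**What to change.** 1. In Section 10.5, replace the closing sentence on the Cohort 3 increase with: *With at least 15 PK-evaluable Cohort 3 participants, the simulated power to find the exposure ratio different from 1 is at least 70% at true ratios 0.5, 0.7, 1.3 and 1.5; this does not apply to the dose rule in Section 3.1 or to confirmation at interim analysis 3 with fewer than 15.*
2. In the first paragraph of Section 10.5, state that the 1.4-fold precision holds on average, as Appendix 7 does.
3. Reconcile Sections 3.1 and 10.5 on one stated scale, so that a reader can see which exposure ratios correspond to the 30% and 50% limits. The limits themselves remain the sponsor's.
4. Optional: if the modelling plan or the second PK interim report does not already give them, tabulate the probability of each zone and of each interim 3 criterion from the existing n = 10 and n = 15 simulations; otherwise cite them. This assumes that the stored output allows it; other sample sizes would probably need new runs.

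Items 1 to 3 are protocol wording and need no additional participants. The cost is that the published assurances read less favourably.

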**Confidential**

## **11 DATA HANDLING**

### **11.1 Data collection**

The investigator/delegate is responsible for ensuring the accuracy, completeness, and timelines of the data reported. All source documents should be completed in a neat, legible manner to ensure accurate interpretation of the data. Data reported in the eCRF derived from source documents must be consistent with the source documents.

eCRF data will be captured via EDC (using the Rave system provided by Medidata Solutions, Inc., a web-based tool). The investigator and site personnel will be trained to enter and edit the data via a secure network, with secure access features (username, password, and identification – an electronic password system). A complete electronic audit trail will be maintained. The investigator/delegate will approve the data (i.e., confirm the accuracy of the data recorded) using an electronic signature (ref. to US 21 CFR Part 11).

Entries recorded by the participant or by the participant's parent(s)/LAR(s) in the Study Drug Diary are considered source data. Site personnel will review and ensure completeness and readability of the participants' entries.

Participant screening and enrollment data will be completed for all participants (i.e., eligible and non-eligible) through the IRT system and eCRF.

For each participant screened, regardless of study treatment initiation, an eCRF must be completed and signed by the investigator/delegate. This also applies to those participants who fail to complete the study. If a participant is withdrawn from the study, the reason must be noted on the eCRF.

